12.2. Statistical Software

Statistical analyses will be performed using SAS Version 9.4 (or higher) for Windows.

The SAS procedures and data steps presented below are only examples of the procedures to be implemented.

The SEEDS are the ones to be used in the procedures.

12.2.1. Single/Multiple imputation

Notes:

Intermittent missing data are imputed by linear interpolation, single imputation

- N=100 imputation samples (variable "_IMPUTATION_") are created prior to next
- step (PROC MI)
 TRTPN='0': refers to placebo treatment arm

12.2.1.1. Placebo (control-based) imputation

RUN;

HELSINN

Macrovariable &VARS includes W_{03} for imputing data at visit 3 weeks, includes W_{03} and W_{06} for imputing data at visit 6 weeks, and so on.

Note: No "Where" clause is used. The model processes ALL records. For the records without any missing data the model does not apply any action.

12.2.1.2. MAR imputation

PROC MI DATA=DATA1 SEED=458122 OUT=DATA2B NIMPUTE=1; BY _IMPUTATION; CLASS TRTPN; VAR TRTPN W_00 W_03 W_06 W_09 W_12 W_15 W_18 W_21 W_24; MONOTONE REGRESSION; RUN;

Note: DATA2B dataset derives from DATA2A (see output dataset from MNAR placebo control-based imputation) after re-setting at missing the assessments as per Exception 1 (see above)

DATA DATAx ; SET DATAx; Where &sel; <<iidentification of the worst value (WORST) for the subject where: At least 2 non-missing: Xlast<X1 Xlast<baseline >> Run: Data Datax2; Set datax; if W 09=. then W 09=WORST; if W 12=. then W 12=WORST; if W 15=. then W 15=WORST; if W 18=. then W 18=WORST; if W 21=. then W 21=WORST; if W 24=. then W 24=WORST; RUN;

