7.2. Sample Size

At the time when the trial was initiated, the primary endpoint was the Composite Clinical Response (CCR) rate. The sample size was determined based on results obtained in patients participating to the previous trials (HT-ANAM-301 and HT-ANAM-302 (4), (5)). The retrospectively observed CCR rates, in the subset of patient with baseline BMI <20 kg/m² and ongoing problems with appetite/eating as defined by inclusion criterion 5, were 20% for anamorelin and 7.5% for placebo at week 12, and 21.0% vs. 6.0% at week 9.

To be conservative the study was adequately powered to detect an improvement in CCR Rate at week 9 from 7.5% in the placebo group to 20.0% for the anamorelin group. This improvement would be detected with 90% power, using a logistic regression for the CCR, with a sample size of 316 patients (158 patients per arm) and a 2-sided 0.05 significance level.

In the latest version (V5.0-V5.A) of the study protocol, co-primary endpoints were defined as follows:

- mean change in body weight over 12 weeks
- mean change in 5-IASS over 12 weeks.

With the fixed sample size of 158 patients per arm, study power was computed by means of simulations based on patients participating to previous company trials comparing anamorelin and placebo. Data from these trials were resampled in an unbalanced and in a balanced way with respect to 5-IASS at baseline (<= or >10), as those studies were not stratified and were unbalanced between treatment groups in terms of 5-IASS. To explore the power of the test procedure for the new endpoint, many scenarios to set assumptions for missing data were simulated, based on choices between different options for the following topics:

- The patient's baseline characteristics of the sample to be obtained (with BMI≤20, ACS-12≤37, 5-IASS≤17, fulfilling inclusion criteria 4 and 5, with/without missing data at baseline, with/without 5-IASS missing at week 3)
- The kind of imputation method adopted (fully MAR or MNAR+MAR based on predefined rules)

- The variables to be included as covariates in the imputations (from a large number to no covariates)
- The process for the MNAR+MAR imputation method: the different sets of subjects contributing to the imputations (all subjects with data vs. all complete subjects) and different sequential steps for applying MAR and MNAR

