10.1.2. Primary efficacy analyses

The primary efficacy analyses will be conducted on the ITT set. Statistical hypothesis H_{0w} and H_{0a} , as defined in Section 7.3, will be tested using an Analysis of Variance (ANOVA) model including treatment group and the three stratification factors at randomization as categorical covariates, at a Type-I error threshold of 0.05 two-sided.

As anticipated in the beginning of this Section 10, inferential analysis will be done after imputation of missing data. An established number (N=100) of imputations will be

performed and for each of the imputation the ANOVA model will estimate treatment effect and the related standard error. The pooling of the estimates will be computed using the Rubin rule (1). The pooled effect and the related p-value will be interpreted for the primary efficacy analyses. In addition, the 95% confidence interval of the pooled difference and the least squares (LS)-mean with the 95% confidence interval will be presented per treatment group.

More details for the multiple imputation process are described in Appendix 12.1.

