This exception is applicable for any reason for discontinuation, when the trend reveals an improvement of the efficacy assessments over time, with the last post-baseline assessment (X_{last}) better than both the baseline and the first post-baseline assessment (X₁). Based on these conditions, it is assumed that the decision of stopping the treatment is not related to the treatment itself (since the efficacy parameter was improving over time). Due to the improvement over time, it can also be assumed that

the treatment effect would have been maintained as it was before interruption for the rest of the observation period. For this reason, the missing values after the treatment discontinuation will be imputed with the Missing at Random (MAR) multiple imputation approach including randomized treatment as the covariate. This approach might be slightly optimistic for values missing at visits far from the visit of the last assessment, however this will not impact the primary endpoint that is limited to week 12, considering that at least assessments at week 3 and at week 6 are requested by the rule.

Imputation for Exception 2

Business & Decision

Life Sciences

This exception is limited to the reasons of treatment discontinuation that are most likely related to lack of efficacy of the treatment; the criterion for considering the unknown values as related to lack of efficacy is the negative trend of the observed efficacy assessments over time, as documented by the last post-baseline assessment (X_{last}) worse than the baseline and the first post-baseline assessment (X_1). Based on these conditions, it is assumed that the decision of stopping the treatment can be related to the treatment itself (lack of efficacy). The missing values will be imputed with the worst value observed for the patient considering only the on-treatment (post-baseline) timepoints.

Final revision of the above rules was done at the BDRM and they have been confirmed.

The details of the process are showed in the following steps.

STEP 1: Single/Multiple imputations

- Impute all intermittent missing data
- Create 100 records for each value
- Application of the Main Rule:

Apply MNAR Control-Based imputation on all subjects (placebo and active treatment) with at least one missing assessment.

- MI on all non-intermittent missing

- only placebo patients contribute to the imputation.

Expectation after imputation: only 1 dataset including:

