- ANAM and placebo patients without missing data (all assessments observed)
- ANAM and placebo patients with at least 1 missing assessment imputed by the imputation process.

Note: it is theoretically possible that aberrant values are derived because of the imputation. Aberrant values are defined as follows:

- For each item of the questionnaires:
 - a) Imputed value < the lower limit (0)
 - b) Imputed value > the upper limit (4)
- \circ For the body weight:
 - a) Imputed value < the lower limit (30 Kg)
 - b) No upper limit for the Body Weight is fixed.

In the cases (a) the imputed value will be set equal to the lower value.

In the cases (b) the imputed value will be set equal to the upper value.

Unscheduled assessments of body weight and questionnaires are not considered for imputations. These values will be listed only (and have all ANL0XFLs set to blank).

 Application of Exception 1: Apply MAR (as correction to the previous control-based imputation on patients fulfilling Exception 1) *Note: Values to be imputed with MAR need first to be re-set at missing.* A flag before starting with the imputation process should identify the cases where the exception 1 should be applied. Imputed values after MAR imputation should be within the aberrant values described above for the MNAR imputation
 According to Exception 2: Impute worst value at subject level.

A flag before starting with the imputation process should identify the cases where the exception 2 should be applied. Worst value should be calculated before any imputation.

- The imputation process does not distinguish between missing due to treatment discontinuation and death. All imputed assessments after death must be set to missing.

No covariates, apart from treatment arm (as by variable or covariate, as relevant) and baseline value will be included in the MI models.

For each variable, 100 imputed values will replace each missing value.

The following variables will be separately imputed according to the above mentioned single or multiple imputation methods:

- Weight
- 5-IASS
- 4-item Anorexia Concerns Subscale (4-IACS)
- 12-item A/CS domain

Business & Decision

Life Sciences

- FAACT total score
- FACT-G total score
- FAACT TOI
- Functional Assessment of Chronic Illness Therapy-Fatigue (FACIT-F)
- FACIT-F TOI score

The PGIS and the PGIC endpoints and the hunger assessment will not be imputed.

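### SAP 12.1.1.2 and 12.2.1 leave the input of each imputation step unclear: as ordered, the Exception 1 MAR model is fitted to placebo-filled values, and Exception 2 may find nothing to fill (minor)

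*SAP*

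**What the plan says.** SAP 12.1.1.2, STEP 1, gives the order:

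1. Interpolate intermittent gaps.
2. Main rule: control-based multiple imputation of every remaining gap in both arms, with placebo patients alone informing the model. The expected result is a single dataset with all gaps filled.
3. Exception 1 (improving patients): "Apply MAR (as correction to the previous control-based imputation on patients fulfilling Exception 1". A note asks for the values of these patients to be set back to missing first.
4. Exception 2 (worsening patients who stopped by physician decision or own withdrawal): impute the patient's own worst on-treatment value. The flag and the worst value are to be fixed before any imputation. No re-set is mentioned.
5. Deaths: "The imputation process does not distinguish between missing due to treatment discontinuation and death"; post-death values are then removed.

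SAP 12.2.1.4 says imputations follow this sequence. For Exception 1, the note in 12.2.1.2 says "DATA2B dataset derives from DATA2A (see output dataset from MNAR placebo control-based imputation) after re-setting at missing the assessments as per Exception 1", while the PROC MI call above it reads DATA1. The example code for the worst-value step has lines of the form "if W 09=. then W 09=WORST" and works on a dataset called DATAx.

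The reason given for Exception 1 is an assumption that "the treatment effect would have been maintained as it was before interruption". SAP 12.2 labels the SAS code as examples.

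**The concern.** A MAR model that carries the pre-interruption effect forward should learn that effect from values actually seen on each arm. After step 2, an anamorelin patient who dropped out and does not meet Exception 1 carries values drawn from a placebo regression. So does a patient who has died, because blanking comes last. In those rows treatment has, by construction, no effect given the earlier visits. Fitting the MAR model to them dilutes the treatment coefficient that Exception 1 relies on.

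Exception 2 has a different gap. If its step runs on the output of step 2, the if-missing condition is never met and the intended lack-of-efficacy penalty disappears.

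The imputed datasets feed both co-primary endpoints and most secondary and exploratory ones (SAP 8.3.1), so two competent programmers could produce different primary results from the same text.

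**Working it through.** **Plan's own figure.** No stated number is contested. The trial size used below does reproduce. For the first endpoint, a change "from 7.5% in the placebo group to 20.0% for the anamorelin group" with 90% power, "with a sample size of 316 patients (158 patients per arm) and a 2-sided 0.05 significance level":

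n = [1.960·√(2·0.1375·0.8625) + 1.282·√(0.075·0.925 + 0.20·0.80)]² / 0.125² = (0.955 + 0.614)² / 0.015625 ≈ 157.4, so 158 per arm.

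**Tracing the order for a trailing gap.**

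| Patient | After main rule | In the Exception 1 fit | At the worst-value step |
|---|---|---|---|
| Exception 1 | placebo-based | re-set to missing, then MAR | not applicable |
| Other anamorelin dropout | placebo-based | counted as observed | not applicable |
| Dead, not Exception 1 | placebo-based | counted as observed | blanked afterwards |
| Exception 2 | placebo-based | counted as observed | not missing, so unchanged |

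**Expected dilution.** If a share f of the anamorelin rows at a visit is placebo-filled, the fitted coefficient is roughly (1 − f)·β, where β is the coefficient from unfilled data.

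**Simulation on a 5-IASS-like score.** 158 per arm; 80 trials × 3 imputations per scenario; both sequences run on the same data. The comparator fits MAR before the placebo fill and applies the worst value to flagged Exception 2 cells. Assumed, because the documents do not give them: effect about 1.3 points (SAP 7.2 has 1.2–1.4); dropout 6, 10 or 15% per three-week interval, so 1 − (1 − h)⁸ = 39, 57 or 73% by Week 24; 30 or 50% of dropouts are deaths; 30 or 20% are physician decision or withdrawal; dropout unrelated to outcome. The contrast is a plain difference in arm means, not the ANOVA with "treatment group and the three stratification factors at randomization as categorical covariates, at a Type-I error threshold of 0.05 two-sided".

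| Dropout; death / Exc. 2 reasons | MAR coefficient, Weeks 9–12: as ordered vs unfilled | Exc. 1 active-arm value, Week 12 | Exc. 2 cells still missing | Exc. 2 value, Week 12 | 12-week contrast: as ordered vs stated rules |
|---|---|---|---|---|---|
| 6%; 30/30 | 0.469 vs 0.567 (−17%) | −0.27 | 0 of 24.7 | +1.46 | 1.093 vs 1.098 |
| 6%; 50/20 | 0.455 vs 0.563 (−19%) | −0.13 | 0 of 17.4 | +1.57 | 1.062 vs 1.065 |
| 10%; 30/30 | 0.376 vs 0.542 (−31%) | −0.21 | 0 of 33.2 | +1.49 | 0.972 vs 0.984 |
| 10%; 50/20 | 0.385 vs 0.553 (−30%) | −0.15 | 0 of 22.7 | +1.98 | 1.014 vs 1.021 |
| 15%; 30/30 | 0.331 vs 0.541 (−39%) | −0.26 | 0 of 43.4 | +1.57 | 0.920 vs 0.929 |
| 15%; 50/20 | 0.365 vs 0.597 (−39%) | −0.30 | 0 of 28.2 | +1.51 | 0.982 vs 0.993 |

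The fall in the coefficient agrees with (1 − f)·β. Cumulative dropout averaged over Weeks 9 and 12 is 19, 31 and 43% at the three rates, a slight overstatement of f because Exception 1 patients are taken out.

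**Size in context.** The contrast shifts by 0.003 to 0.012 points. Against 1.2 points that is at most 0.012/1.2 = 1%. Pairing 1.2 points with 78% power at 158 per arm implies an SD of 1.2·√79/(1.960 + 0.772) ≈ 3.90, hence a standard error of 3.90·√(2/158) ≈ 0.44. The largest shift is under 3% of that.

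**Weight.** A separate simulation (120 trials × 6 imputations per scenario; assumed 5–12% dropout and 3–6% deaths per interval) gave Week 12 changes for Exception 1 patients on anamorelin of 2.67 vs 2.87, 2.62 vs 2.80 and 2.62 vs 2.76 kg, which is 0.14–0.20 kg lower as ordered. The co-primary contrast moved about 0.003 kg, against a planned 1.8 kg (under 0.2%).

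**The case against.** A reader might infer that neither exception is delivered. The documents do not support that.

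- **Exception 1 is applied.** Its patients are re-set and imputed with treatment and their own earlier visits in the model. At most the coefficient is diluted.
- **DATA1 may be the unfilled data.** If it is the interpolated dataset before the main rule, the MAR fit is clean and the fault is a wrong note. The control-based code block, where DATA1 might be defined, is not legible in the text reviewed; that is not a fault of the plan. Even so, such a call would also fill every other patient's gaps under MAR, and no step says that only flagged patients take these draws.
- **Exception 2 is plainly meant to overwrite.** The flag and worst value are fixed before imputation. The example code's selection test (at least two non-missing values, the last below the first) makes sense only on unfilled data. So failure of the executed program is not shown. What remains is an undefined input and a missing instruction, in contrast to the explicit re-set for Exception 1.
- **The code is only illustrative.** True, but the step order is narrative text, and 12.2.1.4 adopts it.
- **A sensitivity analysis already ignores the exceptions (SAP 10.1.3.1).** It shows the result without them, but it cannot tell one implementation of the exceptions from another.

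**Conclusion.** The point stands as a minor specification defect. On the written order and the note, the Exception 1 model treats placebo-based values, some of them after death, as observed anamorelin data, which is at odds with the rationale given for that exception. The code and the note disagree on the input dataset. Exception 2 would be inert if run on the main-rule output, and the text does not say what it runs on.

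A reader might also infer that the primary result would be materially distorted. The figures do not support that: about 0.003 kg and 0.003–0.012 points. Directions are mixed. The Exception 1 dilution works against the drug; leaving Exception 2 cells at placebo-based values favours those patients in whichever arm they sit. The net simulated 5-IASS shift was slightly downward.

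All sizes rest on assumed dropout, death, covariance and reason-for-stopping rates. No Monte Carlo error is attached, so read them as orders of magnitude. The case for acting is reproducibility and agreement with the SAP's own rules.

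**What to change.** In SAP 12.1.1.2 and 12.2.1, preferably before the treatment code is released:

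- Name the input and output dataset of every step, and resolve the DATA1/DATA2A conflict.
- Fit the Exception 1 MAR model to observed plus interpolated data before the control-based fill, with post-death visits excluded from the fit. Take its draws only for flagged Exception 1 patients.
- State that Exception 2 cells are overwritten by the pre-imputation flag, or re-set to missing before the worst-value step.
- Keep the final blanking of post-death values as a safeguard.

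The cost is one paragraph of SAP text and a reordering of existing SAS steps. It needs no new data and no change to the rules themselves.

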12.2.1.3. Worst value imputation

&sel = selection of reason for discontinuation in ("withdrawal by subject", "physician decision")

12.2.1.4. *Combining the imputations*

Imputations will follow the sequence as specified in Section 12.1.1.2.

Values imputed after a patient died will be re-set to missing (which guarantees to have no response after death, as a missing value in SAS is below any value, including the threshold).

Imputed values that are outside the range of the parameter will be set to the relevant limit of the range.

12.2.2. Data Analysis

Each of the imputations will be analyzed by usual SAS procedure.

For the primary efficacy analyses and for the other analyses based on ANOVA, the pooling will be done as follows:

```
/** Model by imputation **/
proc mixed data=[imputed dataset] ;
    by _IMPUTATION_ ;
    class TRTPN(ref="0") [classCovariates];
    model meanchange_w = [COVARIATES] TRTPN ;
    lsmeans TRTPN / cl diffs ;
    estimate 'Anamorelin - Placebo' trtpn 1-1 /cl;
    ods output LSMEANS=MIlsmeans;
    ods output estimates=MIancova;
run ;
```

12.2.3. Pooling of the analysis

The results of the analysis will be summarized with SAS ® PROC MIANALYZE.

```
/** perform the pooling **/
proc mianalyze data= MIancova all ;
    modeleffects estimate ;
    stderr stderr ;
    ods output parameterestimates= ANCOVADIFFS_OUT;
run ;
The output dataset MIIsmeans can be used to obtain the LSmeans by treatment,
by using the relevant proc myanalyze, as follows:
proc sort data=MIIsmeans; by trtpn; where effect='trtpn'; run;
proc mianalyze data=MIIsmeans_&var.;
    modeleffects Estimate ;
    stderr stderr ;
    ods output parameterestimates=ANCOVAls;
    by trtpn;
```

run;

For the Responder analyses the following approach will be implemented.

```
*From Ratitch's paper 'Combining Analysis Results from Multiply
Imputed Categorical Data' PharmaSUG 2013 - Paper SP03;
    ***Log-transform odds ratio estimates;
    data lgodds_t;
        set lgodds (where=(index(effect,"TREATMENT")));
            or_lg=log(oddsratioest);
            or_lg_se =(log(uppercl)-log(lowercl))/(2*1.96);
        run;
    ***Combine transformed estimates;
    PROC MIANALYZE DATA=lgodds_t;
        ods output parameterestimates=or_lg;
```

59/66

T AN001 Effective Date 25 JUL 2022 Approved Version 2.00

```
modeleffects or_lg;
stderr or_lg_se;
run;
***Back-transform combined values;
data or;
set or_lg;
OR_pool =EXP(ESTIMATE); *Pooled Odds Ratio;
OR_pool_L=OR_pool*EXP(-1.96*STDERR); *Pooled lower limit;
OR_pool_U=OR_pool*EXP( 1.96*STDERR); *Pooled lower limit;
run;
```

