4. STUDY DESIGN

4.1. Study Design

Weight loss and anorexia (including appetite loss) represent common and debilitating manifestations in patients with advanced NSCLC. Despite the high prevalence and the association with diminished life-expectancy, the therapeutic advance in managing these symptoms has been so far limited and the treatment of malignancy associated weight loss and anorexia in cancer patients remains an area of highly unmet medical need.

The study is a multicenter, randomized, double-blind, parallel-group, placebocontrolled study to evaluate the efficacy and safety of anamorelin HCI. A total of 318 patients with advanced NSCLC with cachexia have been randomized 1:1 to anamorelin HCI 100 mg or placebo, taken orally once daily (QD) for a total of 24 weeks. Patients were instructed to take the study drug at least 1 hour before their first meal of the day. For each patient the study lasted up to approximately 27 Weeks, including the following:

- A screening period from Day -7 to -1 (on-site Visit 1)
- A 24-week treatment period (on-site Visit 2 to Visit 10)
- A 2-week follow-up period (telephone Visit 11)

A patient is defined as having completed the Study if the follow-up visit (Visit 11) was completed.

The study being placebo-controlled, all comparisons for the efficacy parameters will be done in order to demonstrate superiority of anamorelin over placebo.

T AN001 Effective Date 25 JUL 2022 Approved Version 2.00

Study Design and Schedule of Assessments

Assessment	Screening				Vis Treatm	sit Day ent Pe	riod				Follow-up Period ²
Day	-7 to -1	1	22 (+3)	43 (+3)	64 (+3)	85 (+3)	106 (+3)	127 (+3)	148(+3)	169 (+3)	183 (+3)
Week	-1	1	3	6	9	12	15	18	21	24	26
Visit	1	2	3	4	5	6	7	8	9	10	11
Informed consent	Х										
Medical history	Х										
Physical exam	Х	Х	Х	Х	Х	Х	Х	Х	Х	Х	
ECOG PS	Х				Х						
Vital signs	Х	Х	Х	Х	Х	Х	Х	Х	Х	Х	
Height and BMI	Х										
Body weight	Х	Х	Х	Х	Х	Х	Х	Х	Х	Х	
12-Lead ECG	Х	Х	Х	Х	Х	Х	Х	Х	Х	Х	
Chemistry/Hematology	Х	Х	Х	Х	Х	Х	Х	Х	Х	Х	
HbA1c	Х					Х				Х	
Urine pregnancy	Х	Х			Х						
Urinalysis	Х				Х					Х	
Administer FAACT questionnaire 12-item A/CS domain only	Х										
Administer FACIT questionnaires ¹ and Hunger Assessment Scale questionnaires		х	x	х	х	х	х	х	х	х	
Administer PGIS questionnaires for body weight and anorexia	Х			Х	Х						
Administer PGIC questionnaires for body weight, anorexia and overall condition [,]				х	х						

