10.1.4.3. Analysis on subgroups of the co-primary endpoint

Similarly to the primary efficacy analyses, analyses will be conducted on the ITT Set based on the subgroups defined in Section 8.6. The statistical analyses and models will be based on the models used for the co-primary endpoints described in Section 10.1.2.

A forest plot presenting point estimates and 95% confidence intervals will be presented for weight and 5-IASS.

10.1.4.4. *Premature discontinuation and retrieved dropouts*

In order to summarize the presence of retrieved dropouts in the data of body weight and 5-IASS, a frequencies for patients who have the last efficacy assessment at the same week as the last treatment given as well as retrieved dropouts patients will be calculated. The number and percentage of patients will be presented for each category, including a sub-category of patients who have the last efficacy assessment at the same week as the last treatment given and who stayed alive during the study. Summaries will be done separately for body weight and for 5-IASS by treatment arm on the ITT set.

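### The example pooling code leaves out the complete-data degrees of freedom, so pooled intervals would be slightly too narrow, noticeably so only if a reported subgroup is small

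*SAP*

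**What the plan says.** SAP 10.1.2 tests both co-primary endpoints with an ANOVA "model including treatment group and the three stratification factors at randomization as categorical covariates". On multiple imputation it says "An established number (N=100) of imputations will be" performed, and the estimates are pooled with Rubin's rule. SAP 12.2.2 fits the model with PROC MIXED in each imputed dataset.

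SAP 12.2.3 then gives two pooling calls: "proc mianalyze data= MIancova all" for the treatment difference and "proc mianalyze data=MIIsmeans_&var" for the LS means by arm. Both list only the estimate and its standard error. Neither contains EDF=, and no other section states which degrees of freedom the pooled t statistic should use.

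The same model and pooling apply to subgroups. For the co-primary endpoints, SAP 10.1.4.3 says "A forest plot presenting point estimates and 95% confidence intervals will be presented for weight and 5-IASS". SAP 10.2.3 plans forest plots for all seven secondary endpoints as well. SAP 12.2 qualifies the code: "The SAS procedures and data steps presented below are only examples of the procedures to be implemented".

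**The concern.** With EDF= absent, PROC MIANALYZE takes the complete-data degrees of freedom as infinite. The pooled degrees of freedom then depend only on the number of imputations and the fraction of missing information. With 100 imputations they exceed what the same ANOVA would have with no missing data at all, which is incoherent. The critical value stays close to 1.96 whether the analysis has 318 patients or 30.

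The direction is fixed: leaving the option out can only narrow an interval relative to the small-sample rule. At stake are the error bars in the smallest subgroup rows, where three levels of treatment line are to be shown for nine endpoints. A small level would look somewhat more precise than it is.

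**Working it through.** The plan states no pooled degrees of freedom and no interval width, so it has no figure of its own to reproduce here.

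**Inputs from the documents**
- m = 100 imputations (SAP 10.1.2).
- N = 318: "A total of 318 patients with advanced NSCLC with cachexia have been randomized 1:1" (SAP 4.1).
- Model parameters: intercept 1 + treatment 1 + treatment line 2 + therapy type 1 + 5-IASS stratum 1 = 6 (SAP 10.1.2, 8.4). ITT residual df: v0 = 318 − 6 = 312.
- Two-sided level 0.05.

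**Assumptions, not in the documents**
- Fraction of missing information g = 0.1 to 0.3, widened to 0.05 to 0.5 as a check.
- Subgroup sizes n. Five parameters are used for n ≤ 100, because a factor that defines the subgroup leaves the model (SAP 10.2.3). The exact count is 4 to 6, depending on the subgroup.

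**Formulas**
- Without EDF=: df_m = (m − 1)/g².
- With EDF= (Barnard-Rubin): df = 1/(1/df_m + 1/df_obs), where df_obs = (1 − g)·v0·(v0 + 1)/(v0 + 3).
- Shortfall in width = 1 − t(0.975, df_m)/t(0.975, df).

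**Without EDF=, at any n**
- g = 0.1: 99/0.01 = 9,900 df, t = 1.9602.
- g = 0.3: 99/0.09 = 1,100 df, t = 1.9621.

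**Worked case, ITT, g = 0.1**
- df_obs = 0.9 × 312 × 313/315 = 279.0.
- df = 1/(1/9,900 + 1/279.0) = 271.4, t = 1.9687.
- Shortfall = 1 − 1.9602/1.9687 = 0.43%.

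**Worked case, n = 40, g = 0.3**
- v0 = 35; df_obs = 0.7 × 35 × 36/38 = 23.2.
- df = 1/(1/1,100 + 1/23.2) = 22.7, t = 2.0700.
- Shortfall = 1 − 1.9621/2.0700 = 5.2%.

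| n | v0 | df with EDF=, g = 0.1 | shortfall | df with EDF=, g = 0.3 | shortfall |
|---|---|---|---|---|---|
| 318 | 312 | 271.4 | 0.43% | 181.3 | 0.56% |
| 159 | 153 | 134.1 | 0.89% | 96.5 | 1.15% |
| 100 | 95 | 83.1 | 1.44% | 61.5 | 1.86% |
| 60 | 55 | 47.6 | 2.53% | 36.0 | 3.26% |
| 40 | 35 | 29.8 | 4.05% | 22.7 | 5.21% |
| 30 | 25 | 20.8 | 5.78% | 16.0 | 7.44% |
| 20 | 15 | 12.0 | 10.05% | 9.3 | 12.90% |

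Over g = 0.05 to 0.5 the shortfall is 0.4-0.8% at n = 318 and 9.5-18% at n = 20.

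**Simulated coverage of a nominal 95% interval** (two arms, MAR, proper normal imputation, m = 100, about 4,000 runs per setting; Monte Carlo standard error √(0.95 × 0.05/4,000) = 0.34 points)

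| n | 10% missing: without / with EDF= | 30% missing: without / with EDF= |
|---|---|---|
| 20 | 94.3 / 96.0 | 95.5 / 97.5 |
| 30 | 94.5 / 95.5 | 94.6 / 95.9 |
| 40 | 93.6 / 94.6 | 94.7 / 95.5 |
| 60 | 94.3 / 94.8 | 95.0 / 95.5 |

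At n = 318 both versions give about 95%.

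A further simulation at n = 20 used placebo-only imputation, nearer to the SAP's main rule, with assumed dropout of 20% and 40% by Week 12 and 1,500 runs. Coverage was 94.5% and 93.6% without EDF=, and 95.7% and 95.3% with it. The fraction of missing information there was only 0.01 to 0.03, which shows how much g depends on assumptions. Neither simulation reproduces the full mix of control-based, MAR and worst-value rules in SAP 12.1.1.2.

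**The case against.** **The code is an example.** SAP 12.2 says so, and the body of the SAP commits only to Rubin's rule with 100 imputations. The final program may set the option. This stands, so the point concerns the specification and does not claim that reported results are wrong. However, SAP 12.2.2 presents the steps as the way pooling will be done, and no other text would lead a programmer to add EDF=.

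**Small subgroups were screened out.** SAP 8.6 keeps only subgroups found numerically feasible at the blinded review. Section 13 drops race, ethnicity, region and fluid retention for inadequate numbers. A reader might still infer that the planned forest plots contain intervals that are materially too narrow. The documents do not support that, because they give no size for any kept level. Nor do they rule it out: no minimum size is stated, and third line or higher could be small.

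**Coverage holds up better than the quantiles suggest.** Taking the small-sample interval as exactly nominal gives theoretical coverage without EDF= of 92.0-92.6% at n = 20 and 93.8-94.1% at n = 40. A reader might take the n = 20 figures as the real loss. Both simulations found less at that size, partly because Rubin's variance is itself somewhat conservative there. With EDF=, the first simulation over-covered at n = 20.

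**Nothing confirmatory turns on it.** This stands. The ITT critical value moves from about 1.96 to 1.97, and subgroup results carry no alpha.

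**The responder code is a different matter.** Its odds-ratio limits use a hard-coded 1.96, which might seem to be the same fault. EDF= would not change those limits, and SAP 8.6 plans no responder analysis by subgroup.

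**Conclusion.** A minor point, worth correcting because correction is almost free. As printed, the code gives the pooled ANOVA intervals (and ANCOVA intervals, if pooled the same way) close to a normal quantile at every sample size.

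The effect on the co-primary ITT tests is negligible. For subgroups it is conditional on size: about 1-2% of interval width at 100 to 159 patients, 2.5-3.3% at 60, and above 5% only at about 40 or fewer. Simulated coverage falls short of 95% by about 0 to 1.5 points.

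These figures rest on an assumed fraction of missing information of 0.1 to 0.3, on hypothetical subgroup sizes, and on the final program following the example code. The documents support neither a claim that any reported subgroup is misleading nor any doubt about the primary conclusion.

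**What to change.** In both PROC MIANALYZE calls (treatment difference and LS means), set EDF= to the residual degrees of freedom of the corresponding PROC MIXED fit, that is, patients analysed minus model parameters. This is 312 in the ITT ANOVA with 318 patients. Set it separately for each subgroup, and for each ANCOVA if those are pooled with the same code. State in SAP 10.1.2 that pooled inference uses the small-sample Rubin degrees of freedom, so that the rule does not depend on example code. Print each subgroup's n on the forest plots.

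The cost is one option per call, one sentence, and marginally wider intervals. ITT p-values rise by a negligible amount.
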